## **E5: Inclusion/Exclusion Criteria**

**Inclusion criteria, therapists.** Any English-speaking outpatient or in-home therapist who works for one of the collaborating organizations and who provides family-based treatment to adolescents in that setting will be eligible to participate. Therapists come from a variety of professional backgrounds (e.g., psychology, social work, counseling).

**Exclusionary criteria, therapists.** Therapists will not be recruited if they are not English-speaking.

**Inclusion criteria, parents.** To be eligible for the study, a parent must 1) be English language fluent, 2) have an adolescent who is expected to remain in treatment with the enrolled therapist for at least six more weeks, 3) possess an Android-based "smartphone" with a data plan, 4) possess, or be willing to set up, an email account; 5) be willing to allow the adolescent receiving treatment to participate in the study; and 6) be willing to allow the adolescent participant to use a smartphone with a data plan during the course of the study.

**Exclusionary criteria, parent.** Parents who do participate in the adolescent's mental health treatment or whose English language fluency is insufficient for using the app and engaging in interviews in English will not be eligible.

**Inclusion criteria, youth.** Any youth aged 12-17 who at the time of recruitment is a participating in in-home or outpatient treatment at a collaborating organization, and for whom

the treatment is expected to last at least 6 additional weeks, is eligible. Youth must also be English-language fluent.

**Exclusion criteria, youth.** Youth who are younger than 12 or older than 17 years of age will not be eligible. Youth who lack English language fluency sufficient to use the app or engage in interviews in English also will not be eligible.

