## **D. RESEARCH DESIGN AND METHODS**

### **D1. Overview.**

This protocol describes procedures for conducting an initial real-world test of VillageWhere (VW) usage among parents and youth to whom the technology will ultimately be marketed, namely, those participating in family-based treatment in which improving parental management of youth behavior is a treatment goal. Generally, improved parental management is a goal when youth present to treatment for an externalizing or other behavioral problem. The study will use a single-group (i.e., all participants will use VW) repeated-measures (i.e., pre- and post-usage) design over either a 2 week (i.e., field test) or a 6-week (i.e., open trial) assessment period (see section DX for more details). The intent of the 2-week field test is to prepare for the 6-week open trial by testing study procedures and to ensure that all software “bugs” are identified and fixed before proceeding to the 6-week open trial.

Clinical outcomes that are expected to show improvements as a result of VW usage (e.g., parental monitoring, use of rewards) will be assessed at both time points, and user satisfaction/acceptability measures will be administered post-usage. Parents and youth will also participate in a qualitative post-usage exit interview as another way of assessing their experiences with the technology and suggestions for improvement.

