## **D2. Collaboration**

The investigators have established collaborative agreements with six mental health provider organizations who serve large numbers of adolescents with moderate to severe externalizing behavior problems (see Letters of Support in Appendix 1). These organizations provide mental health services to this population using a range of treatment modalities. Youth are generally allocated to a particular level of service based on problem severity. For example, an adolescent engaging in truancy and rule-breaking behavior may be offered participation in once-weekly multiple family group therapy (i.e., several parent-youth dyads meet together for improved parental management of behavior); a youth abusing substances may receive once-weekly individual and once-weekly dyadic (parent-youth) outpatient sessions; and youth with criminal arrest histories may receive multiple in-home family-therapy oriented treatment sessions each week (i.e., Multisystemic Therapy). These modalities are reflective of current standards of care for youth with varying severities and types of externalizing behavior problems. A common component of each of these modalities is a strong emphasis on parental involvement in treatment and a focus on improving parental management of youth behavior, consistent with the empirical literature regarding what makes treatments for youth externalizing behavior problems effective.

Our partner organizations, located across the U.S., are as follows: Advanced Behavioral Health (ABH; Connecticut); Catholic Charities (Western New York State); Children's Village (New York City and New Jersey); the Maryland Innovations Institute (Maryland); the Portland DBT Institute (PDBTI); and the University of Washington Public Health and Justice Policy Center. Collectively, these organizations employ over 200 mental health therapists who serve youth with externalizing and other behavior problems. We will recruit therapists, parents, and youth to participate in the study from this pool.

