We will develop a 3-4 minute informational animated video that explains the study to those parents deemed likely eligible by therapists. At an appropriate time during or immediately following a clinical session, enrolled therapists will provide a brief introduction to the study and ask the parent to watch a video to learn more about it. The video will be available on YouTube and accessible by hyperlink. The parent can watch the video on the therapist's computer or smartphone or, if the parent prefers, the therapist can email the hyperlink to the parent so that s/he may watch the video at their convenience. Any parent who does not watch the video with the therapist will be given a flyer by the therapist that contains the URL for the video (included as Appendix 4, Family Recruitment Flyer). The purpose of the video is to ensure that all parents approached receive the same information about the study in a standardized way, to minimize the referral burden to therapists, and to minimally interfere with the clinical session. A video also has the advantage of conveying basic study information verbally (rather than in written format as

in on a flyer or through email), which may be helpful if parental literacy is poor. The video will be animated to make it enjoyable and engaging to watch. The script that will be used in this recruitment video is included with this protocol as Appendix 4 (Script for Family Recruitment Animated Video).

To encourage parents to consider participation, we will provide an incentive for watching the video. Specifically, after the parent watches the video, a prompt will pop up that will ask him/her to click on a link to be entered into a lottery to win a tablet computer. The link will open to a secure RedCap interface that will ask the parent to provide his/her name and contact information, including email address, to be notified if they win the lottery drawing. Once the parent enters the information, s/he will see a screen that says,

“You have earned one ‘virtual raffle ticket’ (one chance to win) for entry in the tablet drawing. The drawing will take place in ESTIMATED MONTH OF DRAWING. We will inform you immediately if you are the winner.”

Then, the parent will be presented with one final question:

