**D.7.2. Procedures: Enrolled therapists with linked parent-youth dyad client participants.** Due to the linked nature of this study's design, procedures outlined in this section pertain only to those enrolled therapists for whom a parent-youth dyad on his/her caseload also was enrolled. Note that there is no pre-usage assessment session for therapist participants.

***Informing therapists of linked dyad enrollment and introductory phone call.*** As soon as a parent and youth on an enrolled therapist's caseload also are enrolled, research staff will call the therapist to inform him/her of such, the approximate date of the start of the family's usage period, and to explain next steps. This phone call, expected to take 20 minutes, will introduce the following points to the therapist and encourage the therapist to read a protocol or watch videos to learn more about each:

- a. Therapists should use an upcoming clinical session to set up the app with the parent, specifically, to type in the youth's existing behavior plan into the Game Plan feature (if a behavior plan already exists in the family) or, if one does not already exist, to create a behavior plan using Game Plan;
- b. In sessions thereafter, therapists should periodically ask the parent how his/her use of VillageWhere is going, to communicate to parents that discussing the app in sessions is welcome and appropriate (see "App Inquiries" section below);
- c. At no time should discussing VillageWhere in a session take precedence over any other clinical issue deemed more important or clinically necessary (i.e., that therapists should always use their best clinical judgment as to whether and how much it is appropriate to discuss the VillageWhere app in the session).
- d. Additional support regarding how to incorporate the app into treatment sessions is available to the therapist if desired. These include a clinical protocol, training videos, and weekly office hours.

***Training on app features and therapist role.*** After the introductory phone call, research staff will email the therapist a clinical protocol document explaining best practices for using the app with parents and youth. The protocol will outline all of the app's features and provide clinical recommendations for how to support the participating family's app use in treatment during the family's testing period.

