The email will also inform the therapist that a series of brief training videos showing and explaining specific app features is available to watch if desired. Some videos will focus on the details of a specific app feature, whereas others will provide general advice for using the app clinically. Each video will have a duration of five minutes or less. Participating therapists may watch all or none of these videos, and can watch them in any order they wish at any point during their participation. The clinical protocol and video segments will be redundant in the information they provide, but will offer the therapist a range of options for obtaining information with minimum burden or time investment.

**Helping the parent set up the youth's behavior plan in the app.** The clinical protocol (and a video segment) will outline to therapists how they should help the parent set up the Game Plan feature of VillageWhere in a regularly scheduled session during the first two weeks of the family's usage period. Therapists will be asked to look at the parent's version of the app on the parent's smartphone and guide the parent through how to enter the behavioral expectations the parent has for the youth (e.g., where the youth should be and what s/he is allowed to do before school, at school, after school, and on weekends) into the app. Helping the parent to set up Game Plan will be an expectation for therapists in both the Field Test (2-week test) and the Open Trial (6-week test).

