**App inquiries.** The app inquiry procedure pertains only to those therapist-parent-youth triads participating in the Open Trial. During the introductory phone call with the therapist, research staff will explain what is expected of the therapist after s/he helps the parent set up the app's Game Plan feature. Specifically, the study procedure is for the therapist to make at least two additional inquiries about the app to the parent (i.e., "app inquiries") during two different regularly-scheduled treatment sessions. Two times during the family's six-week app use testing period (during weeks 3 and 4), therapists will receive an email asking them to inquire about the family's app use during a session this week, if clinically and logistically possible. Emails will be similar to the following: "This is a friendly reminder to please make your FIRST (SECOND) "app inquiry" with your linked parent during a session this week, if you have not already done so. Remember that an app inquiry involves simply asking your linked parent if s/he has any questions about the VillageWhere app or wants any help with it. As always thanks for helping with the VillageWhere project, and contact us if you need anything. Research Team."

The purpose of app inquiries is to ensure that the linked parent is explicitly invited to obtain support in using the app as part of treatment, but does not experience pressure from the therapist to use or discuss the app. Therapists will be asked, as part of their post-usage assessment battery, whether or not they discussed the app in treatment and if so, how extensive was the support provided. We expect natural variability on this dimension and will examine this variable's association to parent and youth usage data and clinical outcomes.

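### E5 as worded excludes the parents the study means to enrol; a lesser point is that the six-week treatment screen is shorter than the 45-day open trial

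*Combined protocol and SAP*

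**What the plan says.** The parent exclusion in E5 makes ineligible "Parents who do participate in the adolescent's mental health treatment or whose English language fluency is insufficient" for using the app and taking part in interviews. The sentence is complete, with no gap or redaction.

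Other sections describe the parents the study wants:

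- D1 gives the target users as "those participating in family-based treatment in which improving parental management of youth behavior is a treatment goal".
- D2 says that the modalities at the partner organizations share "a strong emphasis on parental involvement in treatment and a focus on improving parental management of youth behavior".
- D4 describes the approach to parents: "during or immediately following a clinical session, enrolled therapists will provide a brief introduction to the study and ask the parent" to watch the recruitment video.
- D7.2 tells therapists what to do in treatment sessions: "Therapists should use an upcoming clinical session to set up the app with the parent". They should "help the parent set up the Game Plan feature of VillageWhere in a regularly scheduled session during the first two weeks" of the usage period. For the open trial, "the study procedure is for the therapist to make at least two additional inquiries about the app to the parent".
- E1 describes the therapists as treating parents and adolescents jointly.

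On timing, D4 and E5 require that treatment be expected to last at least six more weeks. In D4 the therapist judges this before approaching the parent. D6.1 gives the open-trial test period as 45 days, starting the day after the second member of the dyad downloads the app. Up to 21 days from baseline are allowed for the download. The post-usage session is set at about day 46. E8b states that every parent and youth will be under treatment for the whole of the study.

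**The concern.** The participation rule appears once in the protocol, and there it is reversed. The six parent criteria in D4 contain no participation rule that could override E5. E4 says nothing starts until both IRBs have approved all procedures, and D1 promises an amendment for anything outside the conditions described. Taken at its word, E5 makes each intended parent ineligible, so each such enrolment departs from the approved text. Participation is also a real screening question: D2 describes services that combine individual with dyadic sessions, so staff need a usable rule for a parent who does not attend.

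The timing point carries less weight. E8b names ongoing treatment, and the reporting of potential harm to the therapist, among its protections if the assessment questions cause distress. For a dyad that only just meets the six-week screen, the nominal post-usage session falls after the period in which treatment was expected to continue.

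**Working it through.** **Exclusion wording.** No arithmetic applies, so the two possible readings are set against the rest of the protocol.

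| Section | What it needs | E5 as written | E5 with *not* inserted |
|---|---|---|---|
| D1, D2, E1 | Parents engaged in family-based, joint treatment | Contradicts | Agrees |
| D4 | Parent reached during or just after a session | Contradicts | Agrees |
| D7.2 | Parent in session for set-up and app inquiries | Contradicts | Agrees |

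As written, the only parents left eligible are those outside treatment, and they could not complete the in-session steps.

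**Treatment window.** Inputs:

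- Screen: 6 weeks × 7 = 42 days (D4, E5).
- Test length: 45 days for the open trial and 14 for the field test (D6.1).
- *d*, days from baseline to the second download: 0 to 21 (D6.1).
- *s*, days from screening to baseline: not given. D5 requires signed original forms before any procedure, so it is unlikely to be zero. Values of 0, 7 and 14 are assumed.

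Checks on the plan's own figures: 2 × 7 = 14 reproduces the field test, and 45 + 1 = 46 reproduces the nominal post-usage day. But 6 × 7 = 42 does not reproduce 45, although D1 and D7.2 call the same period six weeks. The difference is 3 days.

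The last test day, counted from screening, is *s* + *d* + 45. Days past the screened window = *s* + *d* + 45 − 42 = *s* + *d* + 3.

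| *s* | *d* = 0 | *d* = 7 (first reminder) | *d* = 21 (limit) |
|---|---|---|---|
| 0 | 3 | 10 | 24 |
| 7 (assumed) | 10 | 17 | 31 |
| 14 (assumed) | 17 | 24 | 38 |

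The nominal post-usage session falls on day *s* + *d* + 46. With *s* = 0, expected treatment at screening would have to be at least 46 days (46/7 = 6.6 weeks) with immediate download, or 67 days (67/7 = 9.6 weeks) at the download limit.

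Field test: the nominal session falls on day *s* + *d* + 15, which is within 42 days whenever *s* + *d* ≤ 27. The timing point therefore mainly concerns the open trial.

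Scheduled therapist tasks: set-up falls in test weeks 1 and 2 and the inquiry reminders in weeks 3 and 4, so they end by test day 28. That is within the window if *s* + *d* + 28 ≤ 42, that is, *s* + *d* ≤ 14.

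**The case against.** The strongest reply on the exclusion is that it corrects itself. Applied literally it would empty the study, every procedural section shows what was meant, and nothing suggests that staff would follow the wording. The screening steps in D4 do not use the sentence, and the parent screening questions are in an appendix that was not available for this review. No endpoint, sample size or analysis depends on it. All of this is fair, and it limits the practical harm. It does not remove the error: the sentence stands in the eligibility list submitted for approval, and no other passage states the rule correctly.

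On timing, six weeks is a minimum and not a typical value. Section A gives 4 to 6 months as the average length of family-based models, and the documents do not say how many dyads would be near the minimum. The 24-day figure needs both the shortest remaining treatment and the slowest permitted download, which the immediate activation emails, the offered help and the reminders in D6.1 all work against. The longer figures rest on assumed screening lags. The session dates are nominal, because D6.1 counts completion within two weeks as timely.

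The safety effect is also limited. The clinically trained research staff remain available, the therapist still has a post-usage battery and interview to complete, and no rule withdraws a dyad when treatment closes. App inquiries are requested only "during a session this week, if clinically and logistically possible". These points stand and make the timing issue minor. They do not make the unqualified statement in E8b correct.

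**Conclusion.** The concern holds. The exclusion in E5 is wrong as written: its literal effect is that no parent who takes part in treatment is eligible. That the cause is a dropped *not* is an inference from the rest of the protocol, which agrees with no other reading. The correction should be made because this is an operative eligibility rule, even though literal application is unlikely.

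The timing gap also holds but would be minor on its own. For an open-trial dyad with exactly 42 days of treatment left and no time between screening and baseline, the test ends 3 days past the window at best and 24 days past at the download limit. Each day from screening to baseline adds one more. The number of dyads affected cannot be worked out from the documents.

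**What to change.** 1. **E5, parent exclusion.** Insert *not*, so that parents who do not take part in the adolescent's treatment are the ones excluded, and add a matching line to the parent criteria in D4. This costs one word and one line, with no downside.

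2. **Treatment window.** Reconcile D4, D6.1, E5 and E8b in one of two ways:
   - Reword the question the therapist already answers, so that it asks whether treatment is expected to last through the dyad's post-usage assessment, allowing for enrolment and download time. Some dyads near the end of treatment would become ineligible (number not known), which could slow recruitment of the 20 open-trial dyads.
   - Leave the screen as it is and correct the sentence in E8b. This loses no dyads.

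3. **Consistency.** Use one description of the open-trial period. D1 and D7.2 call it six weeks, while D6.1 gives 45 days.

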## **E6. Sources of Materials**

- *Describe the research material obtained from living human subjects in the form of specimens, records, or data.*
- *Describe any data that will be recorded on the human subjects involved in the project.*
- *Describe the linkages to subjects, and indicate who will have access to subject identities.*
- *Provide information about how the specimens, records, or data are collected and whether material or data will be collected specifically for your proposed research project.*

All data collected will be for the purpose of this research study only. Sources of data include participant self-report questionnaires, phone app usage data, daily satisfaction ratings, and a qualitative exit interview. Responses to questionnaires will be recorded either on secure online REDCap questionnaires (for research sessions that occur by telephone) or on paper (at participant's request); ultimately all questionnaire responses will be entered electronically by research staff. Data files will be uploaded / transferred from REDCAP to a secure password-protected MUSC homeroom drive and stored. At all stages of collection, entry, storage, and analysis, data will be linked to participants using only arbitrary participant ID numbers. Access to the master electronic file that links participant names to ID numbers will be accessible only to research staff on a secure MUSC homeroom drive; both the drive and the file will be password protected.

## **E7. Potential Risks**

- *Describe the potential risks to subjects (physical, psychological, social, legal, or other), and assess their likelihood and seriousness to the subjects.*
- *Where appropriate, describe alternative treatments and procedures, including the risks and benefits of the alternative treatments and procedures to participants in the proposed research.*

Because therapists will be recruited through the organizations in which they work, there is a risk that therapists will feel pressure to participate because their employer is collaborating with the study. Similarly, because parents and youth will be told about the study by the adolescent's therapist, there is a risk that parents and youth will feel pressure to participate in order to please the therapist.

Actual risks of participation in the study are minimal. Other than survey exit-interview completion, the activities of therapists will be similar to those performed in the context of their employment (i.e., recommending interventions to clients and learning how to implement them). Therapists will not reveal any personal information about themselves other than demographic information, and will not be asked distressing questions, only their opinions about the new technology.

Risks to parent and youth participants include 1) possible distress when answering questions related to individual and family functioning; 2) conflict between the parent and adolescent regarding app usage (e.g., youth resents increased monitoring of his/her behavior by parent); 3) embarrassment if their answers to questionnaires were revealed to others; and 4) embarrassment or concerns about ramifications if app-generated data were to become known to outside sources.

Ways of mitigating these risks are outlined below in the next section, adequacy of protection against risk.

